Our primary outcome is the patient-reported usability and experience when using the mirror. Our secondary outcome is the average time needed to set up the mirror and self-catheterize. These measures will be obtained for all patients and compared between the modified mirror and the standard mirror.

We expect that participants will be in this research study during two weeks of their inpatient rehabilitation stay at the Shirley Ryan AbilityLab, spanning two phases of testing that will each last up to 1 week.

Version Date: 11.22.2021 Page 2 of 10 HRP-593 / v05202020

STUDY INTERVENTION(S) / INVESTIGATIONAL AGENT(S):

We have developed modifications to a standard catheter mirror, which are intended to improve stability and visibility during the self-catheterization procedure for women with motor impairments and urinary retention related to spinal cord injury or other medical conditions. The modified mirror (**Figure 2**) features the standard catheter mirror, held in a surrounding case, with adjustable straps for suspension between the legs whether the individual is in a seated position, reclined, or in a standing position. This also provides flexibility for the mirror's angle to be manipulated for better viewing. The mirror also features LED lights that can be turned on to improve visibility, so that individuals may view the urethral opening easier during catheterization.

Figure 2. The modified self-catheterization mirror system includes the standard mirror, held in a surrounding case, with adjustable straps for suspension between the legs and LED lights that can be turned on/off.

All modified self-catheterization mirrors will be stored in a locked area at Shirley Ryan AbilityLab and will only be accessible to immediate study team members.

PROCEDURES INVOLVED:

Screening: This study will involve recruitment of female patients participating in self-catheterization at the Shirley Ryan AbilityLab (SRAlab). Clinicians at this location will be informed of the inclusion and exclusion criteria for this study in order to refer appropriate patients to the study. Potential research subjects will be referred to authorized research personnel and will also be identified based on inclusion and exclusion criteria using the Cerner application.

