Testing: There will be two phases of the testing, with each phase lasting up to 1 week. **Phase 1** will test their experience with the standard mirror, and **Phase 2** will test their experience with the modified mirror. This order is determined so that all participants attain practice with self-catheterization and study procedures with the standard mirror first, in alignment with the standard of care. The modified mirror will not be given to the participants until Phase 2 testing begins.

Phase 1 (Standard mirror): Subjects will self-catheterize every 4-6 hours, depending on their physician's orders, using the standard mirror. This will allow the subjects to self-catheterize at different times of the day and in various positions. This mirror will have already been provided for self-catheterizing patients by the hospital, and patients will have been trained to self-catheterize by their standard care team.

Version Date: 11.22.2021 Page 3 of 10 HRP-593 / v05202020 Subjects will be given a log sheet specifying the catheterization trial number and the assigned mirror. For each catheterization, subjects will record the position used, the mirror used, and the time it took to complete mirror set up and successfully insert a catheter. They will record this information after each catheterization within the phase.

Phase 2 (Modified mirror): Upon completion of Phase 1 testing, subjects will be trained to use the features of the modified mirror in a single training session. Study staff will demonstrate the attachment of the mirror and help the subject practice the attachment and use of the mirror in any of the positions (seated, reclined in the patient's hospital bed, and standing). If a subject is unable to achieve and maintain a position independently or with minimal assistance, the training in that position will be skipped. Study staff will confirm any positions that the subject uses to self-catheterize (confirmed against the Phase 1 log sheet), and train the subject to utilize the modified mirror in those positions. Training will be considered successful if the subject can set up the modified mirror 3 times independently in all possible self-catheterization positions. At the end of the training session, the subject will be asked if they would be comfortable using the mirror independently.

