A subsequent training session will be scheduled if the subject (1) cannot set up the modified mirror 3 times independently in their possible self-catheterization positions, or (2) does not feel comfortable using the mirror independently. If the subject does not meet these criteria after a second training session, they will be asked to fill out a questionnaire regarding their experience with the device (see "Questionnaires" below) and study procedures will end; patients who do not complete a successful training session will not be invited to complete Phase 2 testing.

Immediately following the completion of a successful training session, subjects will begin the Phase 2 testing, following identical procedures as in Phase 1 but asked to use the modified mirror. Subjects will record the mirror used, position, and time for self-catheterization in a new log sheet. Subjects will continue to have the standard mirror during this phase, and will be encouraged to use this standard mirror instead for any trial if needed for successful self-catheterization.

Questionnaires: Subjects will complete a questionnaire (System Usability Scale) at the end of each testing phase related to self-operation and user satisfaction with the use of the assigned mirror. They may also complete these questionnaires at the completion of the study.

DATA AND SPECIMEN BANKING

Data will be collected and kept confidential and compliant with HIPAA requirements. All personal information and study documentation that can identify participants will be kept secure to protect their privacy and will never be shared at any time with any person or entity. Data collected during the study and shared with others will reference participants only by an alphanumeric code (i.e., de-identified). The "master list" linking personal information to the alphanumeric code will not be shared. Electronic data will be stored on a secure and password-protected network and devices managed by the Shirley Ryan AbilityLab. Electronic folders will be private with limited access as determined by the PI.

Version Date: 11.22.2021 Page 4 of 10 HRP-593 / v05202020 De-identified data will be stored indefinitely. If participants give written consent to be contacted for future studies, this information will be kept separate from de-identified data files, in locked cabinets accessible only by authorized research personnel. All other information will be destroyed in accordance with HIPAA and IRB compliant guidelines.

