SHARING RESULTS WITH PARTICIPANTS

Participants will be recording their own results in a time log, as well as providing their own experiences and satisfaction with the use of a modified mirror during self-catheterization. There is no intent to share additional information about results with participants.

STUDY TIMELINES

- Subjects will each participate in the study for two testing phases, each lasting a period of up to 1 week
- This study will enroll participants for up to 9 months.
- This study is projected to be completed by June 2023

INCLUSION AND EXCLUSION CRITERIA

Inclusion Criteria:

- Females age 13 or older
- Urinary retention related to spinal cord injury or other medical conditions resulting in need for catheterization
- Individuals with sufficient upper limb function to catheterize independently or with minimal assistance, or as deemed appropriate for the study by the Principle Investigator.

Exclusion Criteria:

- Individuals younger than 13 years old
- Individuals with cognitive deficits or visual impairments that may impact safe use of the devices used
- Severe ROM restrictions of the upper and/or lower extremities
- Pregnant

RECRUITMENT METHODS

This study will involve recruitment of individuals who require self-catheterization due to urinary retention related to spinal cord injury or other medical conditions. Clinicians at Shirley Ryan AbilityLab (18th-25th floors) will be informed of the inclusion and exclusion criteria for this study for the referral of appropriate subjects. Potential subjects will be screened and evaluated by the research team. Clinicians on the 18th-25th floors will be trained on the use of the modified mirror and will help introduce the modified mirror to eligible and willing participants.

COMPENSATION FOR PARTICIPATION IN RESEARCH ACTIVITIES

Participants will be compensated up to \$20 for their participation through the ClinCard system. When a subject completes participation, funds will be approved and loaded onto the card. These funds are provided for the subject's participation in the study.

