The PI of the study is required to be notified promptly in the instance of any injury or illness inflicted on the participant as a result of the study. The hospital [Researchers, Shirley Ryan AbilityLab, Northwestern University and all affiliated clinical sites] will not pay for medical care required because of a bad outcome resulting from participation in this study. However, the subject may still seek to get paid back for care required because of a bad outcome resulting from participation in this study.

ECONOMIC BURDEN TO PARTICIPANTS

Subjects will be compensated for their participation in the study.

CONSENT PROCESS

Before recruitment and enrollment onto this study, the participant will be given a full explanation of the study and will be given the opportunity to review the consent form. Each consent form must include all the relevant elements as approved by the Northwestern University Institutional Review Board.

Trained research personnel will guide the participant through consenting process. Participant will be given detailed explanation of the purpose, time line, commitment, procedures, data handling, and privacy and confidentiality of information pertaining to the study. Once this essential information has been provided to the participant and the investigator is assured that the participant understands the implications of participating in the study, the participant will be asked to give consent to participate in the study by signing an IRB approved consent form. Subjects will be consented with a new consent form if changes are made to the protocol. Prior to participation in the trial, the written informed consent form must be signed and personally dated by the participant or authorized guardian and by the person who conducted the informed consent discussion.

The consent process will take place at the Shirley Ryan AbilityLab in Room 11-1401 or on an AbilityLab floor (patient room or private meeting space).

PARTICIPANTS WHO ARE NOT YET ADULTS (infants, children, teenagers)

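### Could participants be shown the modified mirror before they have rated the standard one?

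*Protocol*

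**What the plan says.** Study Endpoints sets the primary outcome: "Our primary outcome is the patient-reported usability and experience when using the mirror". It is compared between the modified and the standard mirror. The SUS is the only questionnaire named.

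Five places bear on when a participant first meets the modified mirror.

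- Recruitment Methods: clinicians on the inpatient floors are trained on the device and "will help introduce the modified mirror to eligible and willing participants". No phase or visit is attached.
- Procedures Involved, Testing: the standard mirror always comes first, and "The modified mirror will not be given to the participants until Phase 2 testing begins".
- Procedures Involved, Phase 2: "Upon completion of Phase 1 testing, subjects will be trained to use the features of the modified mirror in a single training session". Study staff give the demonstration.
- Procedures Involved, Questionnaires: "Subjects will complete a questionnaire (System Usability Scale) at the end of each testing phase", about the mirror assigned in that phase. A further completion is optional: "They may also complete these questionnaires at the completion of the study".
- Study Intervention(s): the modified mirrors are kept under lock, and only the study team itself can reach them.

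**The concern.** The recruitment sentence stands next to referral and screening and speaks of eligible and willing participants, which suggests the enrolment stage. Taken alone, it would let a clinician show the new device before a participant has used the standard mirror under study conditions, or at least before she has rated it.

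The rating is subjective, and she knows which mirror she is using. Seeing a replacement with lights and straps might make the ordinary mirror seem worse, and the apparent gain would grow. All participants follow the same sequence, so no reverse-order group exists to balance or reveal such a shift. The protocol does not ask for the date on which the device was first seen, so an analyst could not adjust for it.

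The end of Phase 1 raises a related question. The SUS and the start of modified-mirror training both fall there, and no sentence makes the first a condition of the second.

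**Working it through.** The question is one of sequence, and the protocol states no figure to reproduce. The check is to set the timing statements side by side.

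1. **Standard-mirror SUS.** It is due when each testing phase ends and concerns the mirror assigned in that phase. The standard-mirror rating is therefore the closing act of Phase 1.
2. **Training.** It is described under the Phase 2 heading and begins once Phase 1 testing is complete. What closes Phase 1 comes before what opens after it, so the ordinary reading puts the SUS before training.
3. **Start of Phase 2 testing.** "Immediately following the completion of a successful training session, subjects will begin the Phase 2 testing". The order becomes: Phase 1 testing, standard-mirror SUS, training, Phase 2 testing, modified-mirror SUS, and then the optional repeat.
4. **Optional repeat.** It is worded as an addition to the end-of-phase questionnaires and does not replace them. Which score is analysed is a matter for the SAP, which is not at hand.
5. **Clinicians' introduction.** This is the only undated step. Two readings fit the rest of the text: a verbal description at recruitment, or help at the hand-over in Phase 2. A physical display before Phase 1 fits less well. The devices are locked away with access limited to the study team, the protocol gives the demonstration to study staff after Phase 1, and participants do not receive the device before Phase 2 testing.

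As to size, let *f* be the share of participants who see the device early and *d* the fall in their standard-mirror SUS. The mean paired difference is then shifted by *f* × *d*. The protocol gives neither quantity. Taking *f* as 0.5 or 1 and *d* as 3 or 5 points, purely as assumptions, the shift runs from 0.5 × 3 = 1.5 points to 1 × 5 = 5 points. With *d* = 0 it is nil. The result only returns what was put in. It shows that a shift would matter if it occurred, and it says nothing on whether one is likely.

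**The case for a change.** The strongest argument for acting is that the rule withholding the device concerns possession and not sight. The protocol's own sequence supports this. In training the participant watches a demonstration and practises attaching the mirror, yet Phase 2 testing begins only after training has succeeded. Some showing and handling before Phase 2 testing is therefore allowed, and the rule cannot by itself bar an earlier look. The locked storage is not a complete answer either, because the floor clinicians are to be trained on the device and so meet it at some point. The remedy would be a sentence or two, with no extra visits or data, and later analysis could not repair the harm.

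Part of this stands. No sentence expressly forbids showing the mirror before the Phase 1 SUS, and the order is implied and not spelled out.

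It does not carry the point further, for three reasons. The handling that the text permits before Phase 2 testing is the training itself, which already follows the end of Phase 1. The recruitment sentence schedules no display, so the route to harm depends on giving its verb the least favourable meaning and on setting aside the storage rule and the assignment of demonstration to study staff. Finally, the added harm is assumed. Under Consent Process, "Participant will be given detailed explanation of the purpose, time line, commitment, procedures", so every participant knows before Phase 1 that a modified mirror is coming. Nothing in the protocol shows that seeing the device shifts the rating beyond being told of it, or in which direction.

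**Conclusion.** The concern does not call for a change. The order of SUS and training is settled by the ordinary reading of the Procedures section. What remains is one undated verb under Recruitment Methods, which can be reconciled with the rest of the protocol and which staff following the whole text would normally handle correctly. A clarifying sentence would only write down an order that the plan already implies.

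The size of any bias is unknown, and the illustrative range above is made of assumed inputs. The conclusion rests on two assumptions: that study staff collect the standard-mirror SUS as the closing step of Phase 1, and that the access rule for the devices is followed. If mirrors were in fact displayed on the floors during recruitment, the concern would regain force, but that would depart from the storage and demonstration arrangements in the text. Expectation raised by the consent discussion, and the fixed order itself, are features of this open, single-sequence design, and dating the introduction would remove neither.

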Version Date: 11.22.2021 Page 5 of 10 HRP-593 / v05202020 For each participant, SRAlab will issue a ClinCard, which is a specially designed debit card for clinical research. Funds will be loaded as appropriate. The funds will be available within 1 day after being loaded and can be used at the participant's discretion. Participants will be issued one card for the duration of the study. If the participant withdraws from the study early, she will be reimbursed for these expenses for the portion of the study that was completed. If the card is lost or stolen, participants may call [contact] or ask a coordinator for a replacement ClinCard.

WITHDRAWAL OF PARTICIPANTS

If a participant has an adverse event, requiring therapeutic intervention and/or the experience interrupts usual daily activities, the subject will be withdrawn from the research study without their consent. This may include injury or impaired skin integrity due to the use of the modified mirror.

If a participant chooses to withdraw from the study, they will be thanked for their time and asked if they wish to disclose why they have decided to withdraw from the study. From that point, all data that was already collected on the participant will be retained and missing data from continued data collection will be treated as a loss to follow up.

RISKS TO PARTICIPANTS

The modified self-catheterization mirror is a prototype device with no significant risk to participants. The device utilizes a standard catheter mirror, enables it to be suspended between the legs, and improves visibility using commercially-available resources such as adjustable straps and miniaturized LED lights. The system can easily be adjusted to fit participants and adhere to different positional needs during self-catheterization. Use of the device can be stopped at any time when completing self-catheterization.

Physical risks from this study may include skin breakdown, urinary tract infection, and muscle soreness.

- Another possible risk is discomfort, skin pressure/friction, or bruising caused by the
 device straps, which has the potential to lead to skin breakdown or abrasions. This risk
 will be minimized by a thorough skin check performed by clinicians before and after
 device use, and application of foam dressings or bandages as needed. Use of the
 modified mirror will be discontinued for any participant with skin breakdown.

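### A woman withdrawn in Phase 2 for an adverse event is not required to give a modified-mirror usability score (low-priority, cheap improvement)

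*Protocol*

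**What the plan says.** STUDY ENDPOINTS sets the outcome: "Our primary outcome is the patient-reported usability and experience when using the mirror". It adds that the measures are to be gathered from every patient and compared between the two mirrors.

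The Questionnaires paragraph of PROCEDURES INVOLVED sets the timing: "Subjects will complete a questionnaire (System Usability Scale) at the end of each testing phase", rating the mirror assigned in that phase. It then allows, without requiring, a further occasion: "They may also complete these questionnaires at the completion of the study". STUDY TIMELINES describes "two testing phases, each lasting a period of up to 1 week", with no minimum length.

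Three rules deal with stopping early in ways that matter here:

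- **Failed training** (PROCEDURES INVOLVED). After a second unsuccessful session, "they will be asked to fill out a questionnaire regarding their experience with the device", and study procedures then end.
- **Adverse event** (WITHDRAWAL OF PARTICIPANTS). For an event "requiring therapeutic intervention and/or the experience interrupts usual daily activities, the subject will be withdrawn from the research study without their consent". The example follows: "This may include injury or impaired skin integrity due to the use of the modified mirror". No questionnaire is attached.
- **Skin breakdown** (RISKS TO PARTICIPANTS). Use of the "modified mirror will be discontinued for any participant with skin breakdown". This stops the device. It does not say that the woman leaves the study.

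**The concern.** The scale is tied to the end of a phase, and a woman withdrawn partway through Phase 2 leaves the study before the planned end of hers. Nothing requires the form at that moment. The protocol does require one when training fails, so the need for a rating at an early exit was recognized, but on one path only. A woman who never began Phase 2 testing is asked about the device. A woman who used it for days and was then withdrawn because it injured her need not be.

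The missing value is the primary outcome, and the reason it is missing can be the device under test. The standard-mirror score was due earlier, at the end of Phase 1, so a Phase 2 withdrawal removes only the modified-mirror half of the pair. If harmed women would have rated the mirror lower, the remaining pairs lean toward it. An analysis plan can say how to treat a missing score, but it cannot recover one that was never collected.

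**Working it through.** **Step 1. Set each Phase 2 exit against the questionnaire schedule.**

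| Path | Source | Modified-mirror questionnaire required? |
|---|---|---|
| Second training session failed | PROCEDURES INVOLVED | Yes, a questionnaire on the device |
| Phase 2 completed | PROCEDURES INVOLVED | Yes, end of phase |
| Device stopped for skin breakdown, woman stays in | RISKS TO PARTICIPANTS | Yes, she still reaches the end of Phase 2 |
| Withdrawn for an adverse event | WITHDRAWAL OF PARTICIPANTS | Not required |
| Leaves by choice | WITHDRAWAL OF PARTICIPANTS | Not required; she is asked for her reason |
| Terminated for a major health change | PROVISIONS TO MONITOR THE DATA | Not required |

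The gap is in the last three rows. The fourth is the one in which harm from the mirror is named as a trigger.

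**Step 2. Would an early score mean anything?** Catheterization is every 4 to 6 hours, so 24/6 = 4 to 24/4 = 6 times a day. After three full Phase 2 days a woman could have used the mirror up to 3 × 4 = 12 to 3 × 6 = 18 times. That is enough experience to rate it.

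**Step 3. Illustrate the size.** The protocol has no figure to reproduce: it gives a sample size of 30 and no event rate or standard deviation. All other inputs here are assumptions.

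- N = women who start Phase 2: 30 at most; 24 assumed if some fail training.
- k = women withdrawn without a score: 1 or 3 assumed.
- G = how much lower their modified-minus-standard difference would have been than the others': 1 to 2 SD of the paired differences assumed.

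If the scored women have mean difference M, the mean over all N is [(N − k)M + k(M − G)]/N = M − kG/N. The available mean is therefore too high by kG/N. Its standard error, in SD units, is 1/√(N − k).

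| N | k | G | Shift kG/N (SD) | Standard error (SD) | Ratio |
|---|---|---|---|---|---|
| 30 | 1 | 1 | 0.033 | 0.186 | 0.18 |
| 30 | 1 | 2 | 0.067 | 0.186 | 0.36 |
| 24 | 1 | 1 | 0.042 | 0.209 | 0.20 |
| 24 | 1 | 2 | 0.083 | 0.209 | 0.40 |
| 30 | 3 | 1 | 0.100 | 0.192 | 0.52 |
| 30 | 3 | 2 | 0.200 | 0.192 | 1.04 |
| 24 | 3 | 1 | 0.125 | 0.218 | 0.57 |
| 24 | 3 | 2 | 0.250 | 0.218 | 1.15 |

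**Step 4. How likely is each k?** For 30 women and an assumed withdrawal risk p, the chance of at least one is 1 − (1 − p)^30: 60% at p = 3% and 79% at p = 5%. The chance of three or more is 6% and 19%. One lost score is thus quite possible, and three are unlikely unless the risk is higher than these values.

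**The case against.** The case against has several parts, and most of it stands as a limit on the point.

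- **A reader might infer that every woman harmed by the mirror lacks a score.** The text does not support that. The skin-breakdown rule stops only use of the mirror. A woman who stays in keeps the standard mirror and still reaches the end-of-phase form, so she is outside the gap.
- **A reader might infer that the protocol rules out an exit score.** It does not. A phase has a maximum length and no minimum, so a stop on day 3 could be read as the end of her phase. A form at study completion is allowed, and the endpoint section intends data from every patient. But no sentence says that withdrawal triggers the form, and staff who follow the text as written could properly omit it.
- **A reader might infer a known or large bias.** Its direction and size are both assumed. A strap abrasion need not lower a rating of self-operation and satisfaction by 1 to 2 SD. The protocol describes the device as carrying no significant risk and requires skin checks before and after use.
- **A reader might infer that the harm goes unseen.** It does not: PROVISIONS TO MONITOR THE DATA requires all adverse events to be documented and reported. Only the usability outcome is affected.
- **How flagged scores enter the comparison is a matter for an analysis plan.** That is right. Only their collection is raised here.
- **Other Phase 2 exits also lack a score.** This is correct, and the fix can cover them.

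**Conclusion.** The point holds in a narrow form. A woman withdrawn from the study in Phase 2 for an adverse event is not required to rate the modified mirror, which fits poorly with the stated intention to obtain the measures from all patients. The likely direction favors the modified mirror, provided that harmed women would rate it lower. The size cannot be established from the protocol. Under the assumed N, k and G, one lost score shifts the mean by about 0.03 to 0.08 SD, less than half a standard error. Three lost scores give 0.10 to 0.25 SD, but that needs an uncommon number of withdrawals. If such withdrawals are rare, the effect is small. This is a cheap improvement of low priority in a 30-woman usability study.

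**What to change.** Leave the withdrawal and device-stop rules unchanged. Add one sentence to PROCEDURES INVOLVED (Questionnaires) and one to WITHDRAWAL OF PARTICIPANTS: a woman withdrawn in Phase 2 for an adverse event is asked, after any care she needs and as her last study step, to complete the System Usability Scale for the modified mirror. She is free to decline, in keeping with the existing permission to skip single questions. Mark the form as an early-stop score.

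The same request can be made of women who leave Phase 2 by choice or are terminated for a health change.

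The cost is two sentences and one existing form. The downside is that the score rests on shorter use than a full phase, which is why it should be marked. Women who decline will still be missing, so the gap is reduced and may not close.
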